### **9.2. Appropriateness of Selected Efficacy Assessments**

The anti-tumor effect of DS-8201a will be assessed by evaluating tumor response according to RECIST version 1.1 as it is generally recognized as standard tumor response criteria.

**10. OTHER ASSESSMENTS**

Not applicable.

## **11. STATISTICAL METHODS**

### **11.1. General Statistical Considerations**

The data-cutoff for the primary analysis will occur after all subjects have either discontinued the study or completed at least 4 cycles of the study drug. After the data-cutoff date for primary analysis, data of interest will be followed for subjects who are still benefiting from the study drug until study completion.

Descriptive statistics will be provided for selected demographic, safety, and PK data by dose level/cohort, if applicable.

- Continuous variables: number of nonmissing observations, mean, standard deviation, median, minimum, and maximum as well as geometric means and geometric coefficient of variation for PK parameters, if applicable.
- Categorical variables: frequencies and percentages.
- Time-to-event variables: number of nonmissing observations (N), median, minimum, and maximum. Kaplan-Meier event rates may also be provided if applicable for specific time-to-event variables.

Assessments of change from Baseline to post-treatment or the ratio of post-treatment to Baseline will include only subjects with both baseline and post-treatment measurements. The last nonmissing value of a variable taken before the first dose of study drug will be used as the baseline value, unless otherwise specified. In general, missing or dropout data will not be imputed for the purpose of data analysis, unless otherwise specified.

Safety analyses will be performed based on the safety analysis set. Analysis of PK parameters will be based on the PK analysis set. Efficacy endpoints will be analyzed based on the efficacy analysis set. Data will be summarized by dose level/cohort.

Data will be listed and summarized using Statistical Analysis System (SAS®) Version 9.4 or higher (SAS Institute, Inc., Cary, North Carolina) according to the Sponsor-agreed reporting standards, where applicable. Complete details of the statistical analyses will be documented in the statistical analysis plan (SAP).

PK parameters will be derived using standard noncompartmental methods using Phoenix WinNonlin® 6.4 or higher (Pharsight Corp., Certara Company, Princeton, New Jersey, United States); and/or SAS Version 9.2 or higher. Graphics may be prepared with SAS® Version 9.2, or higher; SigmaPlot® 12.5, or higher (Systat Software, Inc., San Jose, California, United States); or Phoenix WinNonlin 6.4, or higher.

### **11.2. Analysis Sets**

#### **11.2.1. Enrolled Analysis Set**

The enrolled analysis set will include all subjects who signed an ICF and were enrolled in the study.

### **11.2.2. Safety Analysis Set**

The safety analysis set will include all subjects who receive at least 1 dose of DS-8201a.

### **11.2.3. Pharmacokinetic Analysis Set**

The PK analysis set will include all subjects in the enrolled analysis set who received at least 1 dose of DS-8201a and had at least 1 evaluable postdose serum concentration of DS-8201a without major protocol deviations or events (eg, incomplete dosing, disallowed concomitant medications, etc.) affecting PK.

### **11.2.4. Efficacy Analysis Set**

The efficacy analysis set will include all subjects who received at least 1 dose of DS-8201a and had both pre- and post-treatment efficacy assessment data.

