### **Efficacy Analyses**

The efficacy analyses will be performed on the efficacy analysis set (all subjects who have received at least 1 dose of DS-8201a and had both pre- and post-treatment efficacy assessment data).

Efficacy endpoints will include ORR (the proportion of subjects who achieve a best overall response of complete response [CR] or partial response [PR]) and DCR (the proportion of subjects who achieve a best overall response of CR or PR or stable disease [SD]), DoR, PFS based on Response Evaluation Criteria in Solid Tumors (RECIST) version 1.1, OS, and best percentage change in the sum of diameter of target lesion(s). The point estimate of ORR and its two-sided corresponding 95% exact binomial confidence interval (CI) will be provided. The analysis of the DCR will be performed in the same manner as the ORR analysis. DoR, PFS, and OS will be summarized using the Kaplan-Meier method with median event time and two-sided 95% CI for the median. Descriptive statistics for the best percentage change in the sum of diameter(s) of target lesion(s) will be provided. A waterfall plot of the best percentage change from Screening in the sum of longest dimensions (SLD) for each subject will be presented.

---

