## **9. EFFICACY ASSESSMENTS**

### **9.1. Assessments for Efficacy Endpoints**

Efficacy assessments will be based on tumor assessments. The same imaging tumor assessment as at Screening by CT or MRI scans will be performed every 6 weeks ( $\pm 7$  days) in the first 24 weeks after Day 1 of Cycle 1 and thereafter every 12 weeks ( $\pm 7$  days) regardless of the delay in dosing. The clinical activity of DS-8201a will be assessed by evaluating tumor response. Tumor response will be evaluated using RECIST version 1.1 (Section 17.4).

CT or MRI (spiral CT or MRI with  $\leq 5$  mm cuts) of the brain, chest, abdomen, and pelvis should be used for tumor assessments unless another modality of disease assessment is necessary for the lesions at Screening. Every effort should be made to use the same assessment modality for all assessments for each subject. However, if there is no brain metastasis at Screening, CT or MRI should only be done when symptoms associated with brain metastasis occur during study period. If no clinical symptoms are observed, brain CT or MRI is not mandatory during study period.

The following efficacy endpoints will be assessed. The efficacy variable(s) will be also evaluated at 18 weeks after Day 1 of Cycle 1:

- ORR (the sum of complete response [CR] rate and partial response [PR] rate)
- DCR (the sum of CR rate, PR rate, and SD rate)
- DoR
- PFS
- OS
- Best percentage change in the sum of diameter(s) of target lesion(s)

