## **11.4. Statistical Analysis**

### **11.4.1. Efficacy Analyses**

The efficacy analyses will be performed for the efficacy analysis set. The efficacy endpoints will include ORR, DCR, and time-to-event assessments including DoR, PFS, OS, and Best percent change in the sum of diameter(s) of target lesion(s).

All efficacy endpoints will be listed and summarized.

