#### DoR, PFS and OS:

DoR is defined as the time from the date of the first documentation of objective response (CR or PR) to the date of the first objective documentation of PD. DoR will be measured for responding subjects (CR or PR) only. Detailed censoring rules for DoR will be specified in the SAP.

PFS is defined as the time interval from the date of the first dose of the study drug to the date of first objective documentation of radiographic PD or death due to any cause. Detailed censoring rules for the PFS analysis will be specified in the SAP.

OS is defined as the time interval from the date of the first dose to the date of death for any cause. Subjects will be censored at the time last known to be alive if the subjects have not been reported to have died by the time of cutoff for the primary analysis.

The time-to-event variables, including DoR, PFS and OS will be summarized descriptively using the Kaplan-Meier method to provide the median event time and the corresponding 95% CI.

Best percent change in the sum of diameter(s) of target lesion(s):

Descriptive statistics for the best percent change in the sum of diameter(s) of target lesion(s) will be provided. A waterfall plot of the best percentage change from Screening in the sum of the longest dimensions (SLD) for each subject will be presented.

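### The efficacy analysis set requires a post-treatment assessment yet serves every efficacy endpoint, so a death before any such assessment drops out of PFS and OS, and ORR and DCR can only rise or stay the same

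*Combined protocol and SAP*

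**What the plan says.** - **Who is in the set.** Section 11.2.4 admits "all subjects who received at least 1 dose of DS-8201a and had both pre- and post-treatment efficacy assessment data". The synopsis gives the same definition. Neither place says what counts as efficacy assessment data. The nearest explanation is in Section 9.1: "Efficacy assessments will be based on tumor assessments".
- **Where it is used.** Section 11.1: "Efficacy endpoints will be analyzed based on the efficacy analysis set". Section 11.4.1: "The efficacy analyses will be performed for the efficacy analysis set". The synopsis agrees: "The efficacy analyses will be performed on the efficacy analysis set". Section 11.4.1 names ORR, DCR, DoR, PFS, OS and best percentage change in target lesions. No endpoint is exempted.
- **What counts as an event.** In Section 11.4.1, PFS runs from first dose to the "date of first objective documentation of radiographic PD or death due to any cause". For survival, "OS is defined as the time interval from the date of the first dose to the date of death for any cause". Neither definition requires a post-treatment assessment when the event is a death.
- **The alternative already in the plan.** Section 11.2.2: "The safety analysis set will include all subjects who receive at least 1 dose of DS-8201a". It is assigned to the safety analyses only.
- **Missing data.** Section 11.1 says that missing or dropout data are in general not imputed. No rule counts a treated subject without an assessment as a non-responder.

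**The concern.** Entry to the set depends on something that happens after treatment starts: the subject must live, and stay in the study, long enough to be assessed. For PFS and OS this conflicts with the plan's own definitions, because the earliest deaths are events by definition but belong to subjects outside the analysed set. The PFS and DoR censoring rules that Section 11.4.1 leaves to the SAP cannot repair this, since censoring acts only on subjects who are in the set.

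For ORR and DCR, a subject with no post-treatment assessment cannot be shown to have a response or stable disease. Removing that subject takes one from the denominator and nothing from the numerator.

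Anti-tumour activity is a secondary objective (Section 2.1.2). About 12 subjects are planned and none may be replaced (Section 4.3), so a single exclusion is visible in the estimates. Section 6.6 marks survival follow-up as not applicable, and the last scheduled visit is 40 (+7) days after the last dose (Section 6.5). Deaths soon after the start of treatment are therefore among those the study is best placed to record.

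**Working it through.** The protocol gives no power calculation, response assumption or rate of missing assessments, so there is no planned figure to reproduce. The check is a reading of the text followed by illustrative arithmetic.

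**1. The text applied to one subject.** Take a subject who is dosed and dies in week 4 with no post-treatment tumour assessment.

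| Question | Source | Answer |
|---|---|---|
| Treated? | 11.2.2 | Yes |
| PFS event? | 11.4.1 | Yes, death from any cause |
| OS event? | 11.4.1 | Yes |
| Post-treatment efficacy assessment data? | 11.2.4 with 9.1 | No |
| In the set analysed for PFS and OS? | 11.1, 11.4.1 | No |

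**2. ORR and DCR without assuming outcomes.** Let 12 subjects be treated, k of them have no post-treatment assessment, and r be responders (or controlled). The reported rate is r/(12−k) = (r/12) × 12/(12−k). The factor is 12/11 = 1.09 for k = 1 and 12/10 = 1.20 for k = 2. If r = 0 nothing changes; otherwise the rate rises.

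**3. ORR and DCR with assumed counts** (6 responders, 9 controlled), using the exact binomial 95% intervals named in Section 11.4.1 (Clopper-Pearson):

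| | All 12 treated | One excluded | Two excluded |
|---|---|---|---|
| ORR | 6/12 = 50.0% (21.1–78.9) | 6/11 = 54.5% (23.4–83.3) | 6/10 = 60.0% (26.2–87.8) |
| DCR | 9/12 = 75.0% (42.8–94.5) | 9/11 = 81.8% (48.2–97.7) | 9/10 = 90.0% (55.5–99.7) |

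**4. PFS and OS.** With one death before any assessment and no earlier event or censoring, the Kaplan-Meier estimate just after that death is 11/12 = 91.7% in all treated and 11/11 = 100% in the set. With two such deaths it is 10/12 = 83.3% against 100%.

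For the median, suppose all 12 subjects have an event. In all treated, the curve equals 6/12 = 0.5 after the 6th event, so the median lies midway between the 6th and 7th ordered times. Without the first death, n = 11: the curve is 6/11 = 0.545 after the original 6th time and 5/11 = 0.455 after the original 7th, so the median moves to the 7th.

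**5. Chance of at least one exclusion.** This is 1 − (1−p)^12, where p is the assumed probability that a treated subject has no post-treatment assessment:

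| p | 1% | 2% | 5% | 10% |
|---|---|---|---|---|
| At least one of 12 | 11.4% | 21.5% | 46.0% | 71.8% |

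One pointer lies in Section 1.2.3. Part 1 of the earlier Phase 1 study treated 24 patients and is reported with ORR 34.8% and DCR 91.3%. The only denominator up to 24 that gives both is 23 (8/23 and 21/23). One treated patient therefore appears to be missing from the denominator, for a reason not stated. Taking p = 1/24 purely as an illustration gives 1 − (23/24)^12 = 40%.

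**The case against.** **The key term is undefined.** Section 11.2.4 does not say tumour assessment, and Section 9.1 lists OS among the efficacy endpoints, so survival status might be read as efficacy data. That reading would keep early deaths in the set. It is possible but weak: nothing in the protocol states it, and the opening sentence of Section 9.1 points the other way.

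**A scan is not strictly required.** Section 17.4 allows clinical examination for lesions that cannot be imaged. This is correct. The condition is the absence of any post-treatment tumour assessment, which is slightly narrower than the absence of a scan.

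**An evaluable denominator for ORR and DCR is a declared choice.** It contradicts no definition, and there is no hypothesis test or efficacy threshold. This stands in part: for ORR and DCR the change is a cheap improvement, while the contradiction proper concerns PFS and OS. The present rule is still uneven. Under Section 17.4.2.7.3, a subject lost after one stable-disease assessment made too early to qualify is not evaluable but stays in the denominator, whereas a subject with no assessment leaves it.

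**The effect is small and rarely triggered.** The first scheduled scan is at week 6 (±7 days). The end-of-treatment scan (Section 6.4) and the extra scan at clinical progression (Section 17.4.2.7.4) retain many early leavers. Entry requires ECOG 0–1 and at least 3 months' life expectancy. The 4.5-point ORR shift compares with an interval 78.9 − 21.1 = 57.8 points wide. Events in all 12 subjects are implausible for OS, given the data cutoff rule and the lack of survival follow-up. All of this stands and limits the weight. The exclusions can also be traced, because disposition is summarised in the enrolled and safety sets (Section 11.3) and deaths are listed (Section 11.4.3.1).

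**Conclusion.** The concern holds. On the natural reading of Sections 11.2.4 and 9.1, PFS and OS leave out deaths that their own definitions count, and ORR and DCR are biased upward or unchanged, never downward.

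Each exclusion is modest in size: a factor of 1.09 on ORR and DCR for one subject in 12, and 8.3 percentage points of early survival for one death before any assessment. The ORR and DCR percentages rest on assumed counts, the median example on complete follow-up, and the exclusion probabilities on assumed rates.

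Subjects who leave alive without an assessment barely affect PFS or OS. DoR is unaffected because it is confined to responders, and best percentage change needs a post-treatment measurement in any case. Efficacy is listed as exploratory in Section 2.3.4 and analysed descriptively, and the primary safety objective is untouched. The point should be corrected but does not threaten the trial's main conclusion.

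**What to change.** 1. In Sections 11.1, 11.2.4 and 11.4.1 and the synopsis, assign ORR, DCR, PFS and OS to all treated subjects (the safety analysis set of Section 11.2.2).
2. State that a treated subject with no post-treatment tumour assessment is not evaluable for best overall response and counts as a non-responder and as not controlled.
3. State that death before the first post-treatment assessment is an event for PFS and for OS.
4. Keep the present efficacy set for best percentage change, the waterfall plot and a sensitivity analysis of ORR and DCR. Define efficacy assessment data there as a tumour assessment.

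The cost is wording in the protocol and SAP. No new data, subjects or procedures are needed. Reported ORR and DCR may be slightly lower.

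A separate consistency point adds no weight to the above. Section 6.4 and Table 17.3 list the end-of-treatment tumour assessment without an interval condition, while Section 17.4.2.8 makes it depend on an 8-week interval followed by an unfilled template placeholder. These passages should be reconciled and the placeholder resolved.

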## **11.3. Study Population Data**

Subject disposition and reasons for treatment and study discontinuation will be summarized at each dose level and in total, if applicable, in the enrolled analysis set and safety analysis set.

Demographic and baseline characteristics such as age, sex, race, ethnicity, baseline ECOG PS, cancer stage, histology will be summarized for the enrolled analysis set, safety analysis set, and efficacy analysis set.

## **11.4. Statistical Analysis**

### **11.4.1. Efficacy Analyses**

The efficacy analyses will be performed for the efficacy analysis set. The efficacy endpoints will include ORR, DCR, and time-to-event assessments including DoR, PFS, OS, and Best percent change in the sum of diameter(s) of target lesion(s).

All efficacy endpoints will be listed and summarized.

#### ORR and DCR:

ORR is the proportion of subjects who achieved a best overall response of CR or PR. The point estimate of ORR and corresponding 95% exact binomial confidence intervals (CIs) will be provided.

DCR is the proportion of subjects who achieved a best overall response of CR, PR or SD. The analyses of DCR will be performed in the same manner as the ORR analyses.

#### DoR, PFS and OS:

DoR is defined as the time from the date of the first documentation of objective response (CR or PR) to the date of the first objective documentation of PD. DoR will be measured for responding subjects (CR or PR) only. Detailed censoring rules for DoR will be specified in the SAP.

PFS is defined as the time interval from the date of the first dose of the study drug to the date of first objective documentation of radiographic PD or death due to any cause. Detailed censoring rules for the PFS analysis will be specified in the SAP.

OS is defined as the time interval from the date of the first dose to the date of death for any cause. Subjects will be censored at the time last known to be alive if the subjects have not been reported to have died by the time of cutoff for the primary analysis.

The time-to-event variables, including DoR, PFS and OS will be summarized descriptively using the Kaplan-Meier method to provide the median event time and the corresponding 95% CI.

Best percent change in the sum of diameter(s) of target lesion(s):

Descriptive statistics for the best percent change in the sum of diameter(s) of target lesion(s) will be provided. A waterfall plot of the best percentage change from Screening in the sum of the longest dimensions (SLD) for each subject will be presented.

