## 6.5. Follow-up

The F/U visit should occur 40 days (+ 7 days) days after the last administration of DS-8201a. If the subject begins another anticancer therapy before the end of the 40 days (+ 7 days), every effort will be made to complete all the F/U assessments prior to commencing the new therapy. In case of unresolved AEs, including significant abnormal clinical laboratory values at the end of study assessment, these events will be followed until resolution or until they become clinically not relevant. If assessments at EOT or treatment period are performed within this period, they can be considered to be the F/U data and there is no need to repeat them. If discontinuation of treatment is decided later than 40 days after the last administration of DS-8201a, there is no need to perform the F/U assessments.

The following information will be collected at this F/U visit:

- Obtain vital sign measurements (systolic and diastolic blood pressure and pulse rate, respiratory rate and body temperature).
- Perform a complete physical examination and record the subject's weight.
- Assess functional status using the ECOG PS scale (Section 17.3).
- Obtain blood samples for clinical laboratories (Section 8.8) and ADA (Section 7.4.1). For subjects with positive ADA at F/U visit, additional serum ADA samples may be collected every 3 months ( $\pm 1$  month) up to 1 year from the last dose of study drug, or if the ADA becomes negative, or if ADA titer becomes less than Baseline (applicable when pre-existing ADA is observed), or if the subject starts another therapy for cancer, or withdraws consent from the study, whichever occurs first. A portion of ADA blood sample from each subject who provides consent will be used for future central lab analysis for SARS-CoV-2 testing once protocol version 5.0 is applied for a subject. SARS-CoV-2 testing will be conducted every 4 cycles from Cycle 4 (Cycle 4, Cycle 8 etc.).
- Obtain a serum or urine sample for pregnancy testing in women of childbearing potential. For postmenopausal subjects (no childbearing potential, as indicated by an elapse of at least 12 months after the last

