#### **6.6. New Cancer Treatment and Survival Follow-up**

Not Applicable.

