Tumor assessment	• o		Every 6 weeks (± 7 days) in the first 24 weeks after Day1 of Cycle 1, and thereafter every 12 weeks (± 7 days)																		•		
Pregnancy test	• c																					•	•
Ophthalmologic assessments	• o								• r													•	
Urinalysis	• c																						
Concomitant medications			• s																				
AEs			• u																				

ADA = anti-drug antibodies; AE = adverse event; BI = before infusion; ECG = electrocardiogram; ECOG PS = Eastern Cooperative Oncology Group Performance Status; ECHO = echocardiography; EOI = end of infusion; EOT = end of treatment; F/U = follow-up; HIV = human immunodeficiency virus; IRB = institutional review board; MUGA = multiple-gated acquisition; PK = pharmacokinetics; SCR = screening; SpO2 = peripheral oxygen saturation

- a The date investigator decides the discontinuation of the study drug (+ 7 days)
- b 40 days (+ 7 days) after the last study drug administration or before starting new anticancer treatment, whichever comes first
- c Latest data within 7 days before registration
- d Latest data within 3 days before administration
- e Within 8 hours BI on Day 1 of each cycle until Cycle 4 and then every 2 cycles until Cycle 8 (ie, Cycle 1, 2, 3, 4, 6, 8)
- f Within 15 minutes at EOI on Day 1 of each cycle until Cycle 4 and then every 2 cycles until Cycle 8 (ie, Cycle 1, 2, 3, 4, 6, 8)
- g After 2, 4, 7 hours from the start of administration ( $\pm$  15 minutes)
- h 24 hours ( $\pm$  2 hours) and 72 hours ( $\pm$  2 hours) after the start of administration
- i If Day 1 of the next cycle is delayed for 3 days or more, or if the subject cannot continue into the next cycle, collect blood sample for PK analysis on Day 22 of this cycle (Cycle 1, 2, 3, 4, 6 and 8)
- j 4 hours after the start of administration ( $\pm$  15 minutes)
- k Within 8 hours BI on Day 1 in Cycle 1 and 2, and then every 2 cycles until the end (eg, Cycle 1, 2, 4, 6, 8, 10, 12, and so on)
- l Latest data within 90 days before registration.
- m Before administration at every 2 cycles from Cycle 3 (eg, Cycle 3, 5, 7, 9, and so on)

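### Duration of response leaves out death although PFS counts it, and a Kaplan-Meier OS median is promised without survival follow-up, which makes OS unreliable in an uncertain direction (minor)

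*Combined protocol and SAP*

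**What the plan says.** **Duration of response.** Section 11.4.1 measures DoR from first documented "objective response (CR or PR) to the date of the first objective documentation of PD". The next paragraph ends PFS at the "date of first objective documentation of radiographic PD or death due to any cause". For DoR, only the detailed censoring rules are left to the SAP; the event itself is fixed in the protocol.

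**Overall survival.** Section 11.4.1 states: "OS is defined as the time interval from the date of the first dose to the date of death for any cause". Subjects are censored when last known alive "if the subjects have not been reported to have died by the time of cutoff for the primary analysis". The synopsis (Efficacy Analyses) adds: "DoR, PFS, and OS will be summarized using the Kaplan-Meier method with median event time and two-sided 95% CI for the median".

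**Follow-up.** Section 6.6, headed "New Cancer Treatment and Survival Follow-up", says only that it does not apply. Section 6.5 states: "The F/U visit should occur 40 days (+ 7 days) days after the last administration of DS-8201a". Footnote b of Table 17.3 places that visit 40 (+7) days "after the last study drug administration or before starting new anticancer treatment, whichever comes first". Section 6.5 also waives the follow-up assessments when discontinuation is decided more than 40 days after the last dose. The last visit is then end of treatment (EOT), within 7 days of the decision (Section 6.4).

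**The concern.** The two event definitions treat the same death differently. A SAP that follows the protocol text would censor a responder's death without documented progression. That treats the subject as someone whose response might have continued, so DoR is lengthened.

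For OS, a Kaplan-Meier estimate needs censoring that is unrelated to prognosis. Here subjects leave routine observation shortly after stopping treatment, mainly because of progression or toxicity. Deaths on treatment and up to the last visit are captured; later deaths enter only if someone happens to report them. Anti-tumor activity is a secondary objective (Section 2.1.2), and Section 3.2.3 names DoR, PFS and OS among its measures, so readers could take both summaries at face value.

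**Working it through.** The plan gives no survival, response-duration or hazard assumptions, so there is no figure of its own to reproduce. Every rate below is an assumption unless a source is named.

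**1. DoR.** With constant competing hazards, if a share s of events is death without documented progression, censoring those deaths multiplies the median by 1/(1 − s).

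| s | Inflation, 1/(1 − s) − 1 | Expected deaths without PD among 6 responders, 6s | P(0 or 1 such death) = (1 − s)^6 + 6s(1 − s)^5 |
|---|---|---|---|
| 5% | 5.3% | 0.3 | 0.97 |
| 10% | 11.1% | 0.6 | 0.89 |
| 20% | 25.0% | 1.2 | 0.66 |

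The number of responders comes from Section 1.2.3. The pooled Part 2 ORR of 48.8% gives 12 × 0.488 = 5.9. The HER2-positive gastric and breast cohorts (48.4% and 61.5%) give 12 × 0.484 = 5.8 and 12 × 0.615 = 7.4. The counts assume that every responder has had a DoR event, so they are upper figures at an early cutoff.

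**2. OS: how the direction depends on the hazards.** In this model the median time to last dose is 6 months, contact stops 40 days after the last dose, and no later death is reported.

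| Median to death, on / after treatment (months) | OS median, full follow-up | OS median, day-40 stop |
|---|---|---|
| 60 / 6 | 13.1 | 27.5 |
| 30 / 12 | 16.8 | 25.0 |
| 12 / 12 | 12.0 | 12.0 |
| 12 / 24 | 17.0 | 12.9 |

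The estimate is too high when the hazard rises after treatment, unbiased when it is equal, and too low when it falls.

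**3. OS: how the direction depends on reporting.** Section 11.4.1 counts any death reported by the cutoff but censors everyone else when last known alive. A late death can therefore enter while a comparable survivor stays censored at the last visit.

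This second model uses exponential time on treatment. A share p of treatment endings are deaths; the other subjects die after a further exponential time. Accrual is uniform over 8 months (Section 3.2.1). The cutoff is 4 × 21 = 84 days after the last enrolment (Section 11.1). Routine contact runs to 47 days after treatment ends. A share q of the later deaths before the cutoff is reported. In every row the hazard is higher after treatment than on it. Entries are 9-month OS, with simulation error of about 0.01.

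| Medians on / after (months), p | True | q = 0 | 25% | 50% | 75% | 100% |
|---|---|---|---|---|---|---|
| 4 / 6, p = 0 | 0.64 | 0.81 | 0.71 | 0.64 | 0.57 | 0.51 |
| 4 / 6, p = 0.3 | 0.51 | 0.57 | 0.53 | 0.48 | 0.45 | 0.41 |
| 6 / 12, p = 0.3 | 0.69 | 0.72 | 0.69 | 0.67 | 0.65 | 0.63 |

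Over eight combinations (4/6 and 6/12 months; p from 0 to 0.3), the upward bias has gone or reversed by q of about 50% to 75%.

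**4. Is the median estimable at the primary cutoff?** The longest follow-up is 8 + 84/30.44 = 10.8 months. In simulated trials of 12 under the same eight combinations with q = 0, the median is not reached in about 67% to 98%. With full follow-up to the same cutoff the range is 48% to 92%. If doses 2 to 4 of the last subject are each delayed by the maximum 28 days (Section 5.4.2), the horizon is 8 + 168/30.44 = 13.5 months. The ranges are then 55% to 97%, and 27% to 86% with full follow-up. The early cutoff is the main reason.

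**The case against.** **DoR.** DoR and PFS are different endpoints, and different event definitions are not in themselves a contradiction. The SAP may settle how deaths are handled. Few subjects are affected. The last argument stands and keeps the point minor. The SAP argument is weak, because the protocol defers the DoR censoring rules and not the event.

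**OS.** Late deaths have other routes into the data: unresolved adverse events and ILD are followed to resolution (Sections 3.2.5.2, 6.5 and 8.2), deaths from progression go on a Death eCRF with no stated time limit (Section 8.5), ADA-positive subjects may give later samples (Section 6.5), and the end-of-study definition mentions telephone contacts (Section 3.2.1). This stands in part. None of these is vital-status follow-up of all subjects, but they undermine any fixed statement about direction. A reader might infer that OS must look too good because deaths are likelier after treatment. The documents do not support that: they give no hazards and do not say how completely late deaths would be reported, and the third table shows the sign changing with reporting alone.

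**The 9-month figures.** Only about 12 × (10.8 − 9)/8 = 2.7 subjects enrol early enough to be followed for 9 months, and landmark rates are optional under Section 11.1. This also stands. The table shows mechanism and sign, not a forecast for this trial.

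**Conclusion.** Both defects are in the text, and both are minor.

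- **DoR:** followed as written, the definition censors a responder's death and lengthens DoR. The inflation of 5%, 11% or 25% rests on assumed shares of deaths without progression and on constant hazards. In practice it would usually concern 0 or 1 of about 6 responders.
- **OS:** the promised median has no systematic follow-up behind it, so the curve is unreliable and its direction uncertain. It is too high if the hazard is greater after treatment and late deaths go unreported. It is about right or too low if roughly half or more of them are reported ad hoc while survivors stay censored, or if the hazard falls after treatment. A one-way upward bias does not follow from the documents.

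These endpoints are exploratory (Section 2.3.4) and descriptive, with no hypothesis test. The primary safety objective is unaffected.

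**What to change.** 1. In Section 11.4.1, define DoR as time from first documented CR or PR to first objective documentation of PD or death from any cause, whichever comes first. This is a wording change; DoR may come out slightly shorter.
2. In Section 11.4.1 and the synopsis, replace the OS median with a count and listing of deaths known up to each subject's last scheduled contact (EOT or follow-up visit), and list later known deaths separately. A fixed 47-day window would not do, because the last visit can fall on day 40 or earlier. Align the endpoint lists in the synopsis and in Sections 2.3.4, 9.1 and 11.4.1. The cost is losing a median that in most of the assumed settings would not be reached at this cutoff.
3. If OS is kept instead, schedule brief vital-status contacts for all subjects up to the primary cutoff under Section 6.6. For about 12 subjects this is a small amendment, and the cutoff need not move.
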